8.4.1.1 Adverse Events of Special Interest

For this study, elevated transaminases events and rash events, as determined by MedDRA PTs in [Appendix F](#), are considered as AESIs.

For treatment-emergent elevated transaminases events and rash events, the following categories will be summarized overall:

- Subjects with events
- Subjects with events by maximum severity
- Subjects with events leading to treatment discontinuation
- Subjects with events leading to treatment interruption

- Subjects with serious events
- Subjects with related serious events
- Subjects with events leading to death
- Duration of events
- Time-to-onset of first event (with the first dose date of TC in the OLE as the reference while calculating time-to-onset)

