8 STATISTICAL ANALYSIS

8.1 General Considerations

The precision standards for reporting safety variables are provided in an internal Biometrics document that specifies the programming rules including the precision for derived variables.

The Schedule of Assessments is provided in Section 3 of CSP.

Continuous variables will be summarized using the following descriptive summary statistics: the number of subjects (n), mean, standard deviation (SD), median, minimum value (min), and maximum value (max).

Categorical variables will be summarized using counts and percentages. Percentages will be presented to 1 decimal place.

The **baseline value**, unless otherwise specified, for the long-term safety analysis will be the **TC safety baseline**, defined as the most recent non-missing measurement (scheduled or unscheduled) collected before the first dose of ELX/TEZ/IVA either in the parent study or the open label study, as applicable. The baseline value for the long-term efficacy analysis, unless otherwise specified, will be the **parent study baseline**, defined as the most recent non-missing measurement (scheduled or unscheduled) collected before the first dose of study drug in the parent study. For assessments collected in duplicate or triplicate, the baseline will be defined as the average of non-missing values.

Absolute change from baseline will be calculated as post-baseline value - baseline value.

Relative change from baseline will be calculated and expressed in percentage as $100\% \times (\text{Post-baseline value} - \text{Baseline value}) / \text{Baseline value}$.

Treatment-emergent (TE) Period will include the time from the first dose date of study drug in the OLE to 28 days after the last dose of the study drug in the OLE or to the date of completion of study participation (as defined in CSP Section 9.1.5), whichever occurs first.

Unscheduled visits: Unscheduled visit measurements will be included in analysis as follows:

- 1) In scheduled visit windows per specified visit windowing rules
- 2) In the derivation of baseline and last on-treatment measurements
- 3) In the derivation of maximum and minimum values during TE period, and maximum and minimum change from baseline values during TE period for safety analyses
- 4) In individual subject data listings as appropriate

Visit windowing rules: The analysis visit windows for protocol-defined visits are provided in [Appendix A](#).

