8.2 Background Characteristics

8.2.1 Subject Disposition

A summary table of subject disposition will be presented for the OL-AS by treatment group in the parent study and overall with the following categories:

- Enrolled (OL-AS)
- Dosed (OL-SS)
- Enrolled and dosed (OL-FAS)

The number and percentage (based on OL-FAS) of subjects in each of the following disposition categories will be summarized by treatment group and overall:

- Completed treatment
- Prematurely discontinued the treatment and the reason for discontinuation
- Completed study
- Prematurely discontinued the study and the reason for discontinuation

A listing will be provided for subjects who discontinued treatment or who discontinued study with reasons for discontinuation.

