8.2.4 Prior and Concomitant Medications

Medications will be coded using the World Health Organization Drug Dictionary (WHO-DD) and categorized as follows:

Prior medication: any medication that was administered during the 56 days before the first dose date of study drug in this OLE study.

Concomitant medication: medication continued or newly received during the TE period in this OLE study.

Post-treatment medication: medication continued or newly received after the TE period in this OLE study.

A given medication may be classified as follows: prior, concomitant, post-treatment, both prior and concomitant, both concomitant and post-treatment, or prior, concomitant, and post-treatment.

If a medication has completely missing or partially missing start/stop date and if it cannot be determined whether it was taken before the first dose date of the OLE, concomitantly during the TE Period for the OLE, or after the TE Period for the OLE, it will be considered in all 3 categories of prior, concomitant, and post-treatment medication. Details for imputing missing or partial start and/or stop dates of medication are described in [Appendix B](#).

For the OL-SS, prior medications and concomitant medications will be summarized descriptively by: 1) treatment group in parent study and overall, Preferred Name (PN); and 2) treatment group in parent study and overall, anatomic class (ATC) level 1, ATC level 2, and PN. Post-treatment medications will be listed for each subject, if applicable.

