8.2.5 Study Drug Exposure

Duration of study drug exposure (in days) will be calculated as: last dose date of study drug in the OLE – first dose date of study drug in the OLE + 1, regardless of study drug interruption.

Study drug exposure (in weeks) will be summarized descriptively by the number of subjects (n), mean, SD, median, min, and max. It will also be summarized by interval (≤ 24 weeks, >24 to ≤ 48 weeks, >48 to ≤ 72 weeks, >72 to ≤ 96 weeks, >96 weeks), using counts and percentages. Additionally, the total study drug exposure, defined as the sum total of the study drug exposure across all subjects (in patient-years), will be provided. Exposure summaries will be based on the OL-SS, and presented overall.

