8.3.2.2 Analysis Method

Absolute change in SwCl from baseline:

The mixed-effects model for repeated measures (MMRM) for the parent study 116-FAS will be same as that described in the SAP for Study 116. In the MMRM for the OL-FAS, the absolute change from baseline in SwCl will be the dependent variable. The model will include treatment group (as randomized in the parent study), visit, and treatment-by-visit interaction as fixed effects, with continuous baseline LCI_{2.5} from the parent study and weight at Screening (<30 versus ≥30 kg) of the parent study as covariates.

The repeated-measures analysis will be based on the restricted maximum likelihood method assuming an unstructured covariance structure to model the within-subject errors. The denominator degrees of freedom will be based on the method proposed by Kenward-Roger⁶. If the model fails to converge due to the unstructured covariance assumption, a compound symmetry covariance structure will be used to model the within-subject errors. In the MMRM approach, assuming that the data are missing at random, no imputation of missing data will be performed.

Results from the 2 MMRMs (for the parent study and for the OE) will be presented in a single summary table. The number of subjects, least-squares means (LS means) for absolute change from baseline at scheduled visits within each treatment group (as randomized in the parent study) along with the corresponding standard error (SE), and 95% confidence interval (CI) will be presented. The LS means (±SE) for absolute change from baseline at each visit will also be plotted by treatment group (as randomized in the parent study).

In addition, the descriptive statistics for raw values and absolute changes from baseline by treatment group (as randomized in the parent study) and OL visit will be presented for the OL-FAS.

Absolute change in LCI_{2.5} from baseline:

Analysis of this endpoint will be based on an MMRM similar to the analysis of the absolute change from baseline in SwCl. A descriptive summary of raw values and absolute changes from baseline will also be presented.

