8.4.1 Adverse Events

For analysis purposes, AEs will be classified as pretreatment AEs, TEAEs, and post-treatment AEs, defined as follows:

- **Pretreatment AE:** any AE before the first dose of ELX/TEZ/IVA in the TE Period in this OLE study
- **TEAE:** any AE that worsened (either in severity or seriousness) or newly developed at or after the first dose date of ELX/TEZ/IVA in the TE Period in this OLE study
- **Post-treatment AE:** any AE that worsened (either in severity or seriousness) or newly developed after the TE Period in this OLE study

For AEs with missing or partial start dates, if there is no clear evidence that the AEs started before or after study drug treatment, then the AEs will be classified as TEAEs. Details for imputing missing or partial start dates of adverse events are described in [Appendix D](#).

An overview of all TEAEs for the OL-SS during the TE Period will be summarized overall and include the following categories:

- Number of TEAEs (total number of TEAEs only)
- Subjects with any TEAEs
- Subjects with TEAEs by strongest relationship
- Subjects with TEAEs by maximum severity
- Subjects with TEAEs leading to treatment discontinuation
- Subjects with TEAEs leading to treatment interruption
- Subjects with Grade 3/4/5 TEAEs
- Subjects with related TEAEs
- Subjects with serious TEAEs
- Subjects with related serious TEAEs
- Subjects with TEAE leading to death

The frequency counts and percentages, as well as the exposure adjusted event rate, will be presented for the above overview table. The exposure adjusted rate will not be presented for strongest relationship and maximum severity categories.

The following summary tables of TEAEs will be presented overall:

- All TEAEs
- Grade 3/4/5 TEAEs
- TEAEs by strongest relationship
- TEAEs by maximum severity
- TEAEs leading to treatment discontinuation
- TEAEs leading to treatment interruption
- Related TEAEs
- Serious TEAEs
- Related serious TEAEs
- TEAEs leading to death

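### Cheap improvement, not an error: show the transaminase and rash summaries, including time-to-onset, by parent-study treatment group beside the planned overall column

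*SAP*

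**What the plan says.** SAP 8.4.1.1 names two adverse events of special interest (AESIs), elevated transaminases and rash. On layout it says: "For treatment-emergent elevated transaminases events and rash events, the following categories will be summarized overall". The listed categories include subjects with events, duration, and "Time-to-onset of first event (with the first dose date of TC in the OLE as the reference while calculating time-to-onset". One clock therefore applies to everyone, and there are no columns by prior treatment.

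Two other places bear on who is in the extension:

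- SAP 8.1 defines the safety baseline as the last measurement "collected before the first dose of ELX/TEZ/IVA either in the parent study or the open label study, as applicable".
- SAP 8.3.2.2 carries the parent arms into the efficacy model: "The model will include treatment group (as randomized in the parent study), visit, and treatment-by-visit interaction as fixed effects".

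Columns by parent arm are already planned for several outputs. On the safety set itself, SAP 8.2.4 says: "For the OL-SS, prior medications and concomitant medications will be summarized descriptively by: 1) treatment group in parent study and overall". For completion and discontinuation, with reasons, SAP 8.2.1 says: "The number and percentage (based on OL-FAS) of subjects in each of the following disposition categories will be summarized by treatment group and overall". Demographics, medical history, compliance and protocol deviations (SAP 8.2.2, 8.2.3, 8.2.6, 8.2.7) use the same layout.

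Safety outputs do not. SAP 8.2.5: "Exposure summaries will be based on the OL-SS, and presented overall". SAP 8.4.1: "An overview of all TEAEs for the OL-SS during the TE Period will be summarized overall". This follows the Protocol Synopsis and Protocol 12.3.4, which say that safety will in general be pooled and will be descriptive only.

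**The concern.** Long-term safety is the primary objective, and these are the only two AESIs. The safety-baseline definition allows the first ELX/TEZ/IVA dose to fall in either study, a provision that would not be needed if every subject had received the combination in the parent study. With randomized parent arms, the natural reading is that the extension combines new starters with subjects who are already exposed. The documents do not state this outright, and they do not give the split.

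If both kinds of subject are present, two summaries lose information:

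- **Time-to-onset.** For a new starter it is time since the first-ever dose. For a pre-exposed subject it is time since rollover, to the first event that is new or worse in the extension.
- **Incidence.** One pooled percentage cannot show separately how often these events follow first exposure.

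A reader who wants to know when transaminase elevations or rash tend to appear after starting treatment could not get that from the planned table.

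**Working it through.** The plan has no figure to reproduce. The 108 in SAP 6.2 is an expected rollover count with no calculation behind it. The comparator, allocation and duration of the parent study and the AESI rates are not in the documents, so every input below except 108 subjects and 96 weeks is an assumption.

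**1. The two clocks.** Let D be the weeks of ELX/TEZ/IVA in the parent study. At extension week w, a new starter has had w weeks on drug and a pre-exposed subject D + w. The ratio is (D + w)/w.

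| Extension week | D = 12 | D = 24 | D = 48 |
|---|---|---|---|
| 4 | 4.0 | 7.0 | 13.0 |
| 8 | 2.5 | 4.0 | 7.0 |
| 24 | 1.5 | 2.0 | 3.0 |
| 48 | 1.25 | 1.5 | 2.0 |
| 96 | 1.13 | 1.25 | 1.5 |

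The two meanings of time differ most, in relative terms, at the early visits. The table shows a difference in prior exposure. It does not show an effect on any safety result.

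**2. Pooled median onset.** Let s be the share of first events that come from new starters. Assume new-starter onset is front-loaded, F(t) = (1 − exp(−t/m))/(1 − exp(−96/m)), and pre-exposed onset is uniform over 96 weeks (median 48). The pooled median t solves s·F(t) + (1 − s)·t/96 = 0.5.

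| New-starter median | s = 25% | s = 50% | s = 75% |
|---|---|---|---|
| 5.5 weeks (m = 8) | 32.5 | 14.9 | 8.1 |
| 11.1 weeks (m = 16) | 35.4 | 22.8 | 15.2 |

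Check for m = 8, s = 50%: at t = 14.9, F = 0.845 and t/96 = 0.155, so 0.5 × 0.845 + 0.5 × 0.155 = 0.50. With the same onset pattern in both groups, the pooled median equals the common median.

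**3. Pooled incidence.** Pooled = f·p(new) + (1 − f)·p(pre), where f is the share of new starters. For 15% and 5% at 54/54 it is 0.5 × 15% + 0.5 × 5% = 10.0%; over splits from 36/72 to 72/36 it runs from 8.3% to 11.7%. Equal risks leave it unchanged. The documents do not say whether the risks differ, or in which direction.

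**4. What the added columns could show.** Exact 95% intervals for one such table: 8/54 = 14.8% (6.6 to 27.1), 3/54 = 5.6% (1.2 to 15.4), and 11/108 = 10.2% (5.2 to 17.5) overall. The group intervals overlap widely. Power to detect 15% against 5% at 54/54 is about 41%.

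**5. Precision given up in each column.** The zero-event one-sided 95% upper bound is 1 − 0.05^(1/n): 2.7% for n = 108 and 5.4% for n = 54. With full exposure, patient-years are n × 96 × 7/365.25, which is 198.7 and 99.4. The bound −ln(0.05)/PY is then 1.5 and 3.0 per 100 patient-years.

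**The case against.** The case for leaving the plan alone is a serious one. The protocol states pooled safety twice, and the SAP applies it consistently to exposure, adverse events, AESIs and laboratory data, while parent-arm columns go to background and efficacy outputs. That looks deliberate. The onset clock is stated openly and matches the treatment-emergent period, so the SAP never offers the figure as time since the first-ever dose. Subject-level adverse event listings are planned (SAP 8.4.1), so onset could be split by prior exposure by hand. Change in liver tests already has a pre-ELX/TEZ/IVA reference for every subject. Group columns would rest on few events.

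Most of this stands, and it rules out some stronger conclusions that a reader might draw:

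- *The overall-only layout breaks the protocol, or the clock is wrong.* Neither is so; both follow the stated plan.
- *The pooled AESI summaries cannot be interpreted.* They can be, as incidence and onset within the extension. The columns make them more interpretable.
- *Pooling dilutes or distorts AESI risk.* The documents give no rates, onset patterns or split, so neither the presence nor the direction of such an effect can be shown.
- *Side-by-side columns would compare new with continuing users.* Protocol 8.1 and 12.1 keep out anyone who permanently stopped study drug in the parent study. Among pre-exposed subjects, that removes people who stopped ELX/TEZ/IVA itself. Columns without a note on this would invite a false comparison.
- *All safety tables need the split.* The all-TEAE overview is not needed in order to read two AESIs.

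What remains is that listings leave the reader to rebuild a split that the SAP already tabulates elsewhere, on an output that serves the primary objective.

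**Conclusion.** The point holds as a cheap improvement. SAP 8.4.1.1 gives AESI incidence and time-to-onset overall only. If the extension mixes new starters and pre-exposed subjects, as SAP 8.1 and 8.3.2.2 imply, the pooled onset figure combines two quantities and first-exposure incidence cannot be seen on its own. Nothing in the plan fails without the change, and no sample size, test or multiplicity rule is affected.

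The possible size runs from zero (same onset pattern and risk in both groups) to a pooled median that moves between about 8 and 35 weeks with the event mix, under the onset shapes assumed above. Those shapes are illustrations and not estimates. The added columns would describe onset and incidence by group; they could not establish a group difference.

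**What to change.** In SAP 8.4.1.1, keep the overall column as the main presentation and add descriptive columns by parent-study treatment group to the AESI summaries, including time-to-onset. Give each column its N, and add patient-years by parent group to SAP 8.2.5 as denominators. Matching columns in the liver-test threshold summary (SAP 8.4.2) are optional. The all-TEAE overview and the other safety tables can stay as planned.

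Add a footnote with three parts:

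- For subjects exposed to ELX/TEZ/IVA in the parent study, onset runs from the first extension dose to the first event that is new or worse in the extension.
- That group excludes subjects who permanently discontinued study drug in the parent study.
- The columns are therefore not a between-group comparison.

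The cost is SAP wording, one footnote and some extra columns. The grouping variable is already in use, no new data are needed, and the protocol's general rule of pooling is kept. The drawback is that group estimates are imprecise, as shown above.

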8.4.2 Clinical Laboratory

For the treatment-emergent laboratory assessments, the observed values and change from baseline values of the continuous hematology, coagulation, and chemistry results will be summarized in SI units overall at each visit during the TE Period for the OLE.

The number and percentage of subjects with test values meeting at least 1 threshold analysis criterion event during the TE Period for the OL-SS will be summarized overall. The threshold analysis shift from baseline will also be summarized for selected LFT laboratory parameters. The threshold analysis criteria are provided in [Appendix E](#).

For selected LFT laboratory tests (alanine transaminase [ALT], aspartate transaminase [AST], alkaline phosphatase [ALP], and total bilirubin [TBILI]), a scatter plot of the maximum treatment-emergent value versus the baseline value corresponding to \times ULN (upper limit of normal) will be presented overall. Furthermore, a scatter plot of the maximum treatment-emergent value of ALT and AST, separately, versus the maximum treatment-emergent value of TBILI corresponding to \times ULN will also be presented.

Results of urinalysis and positive urine/serum pregnancy test will be listed in individual subject data listings only. For positive serum pregnancy listing, subjects with serum HCG which are abnormally high will be selected.

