9.2 Method of Assigning Subjects to Treatment Groups

This is an open-label study.

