12.3.4 Safety Analysis

The primary objective of the study is the evaluation of the long-term safety and tolerability of ELX/TEZ/IVA. All safety analyses will be based on the TE Period in this open-label study for subjects in the OL-SS, unless otherwise specified.

The overall safety profile of study drug will be assessed in terms of the following safety and tolerability endpoints:

- Incidence of treatment-emergent adverse events (TEAEs)
- Clinical laboratory values (i.e., serum chemistry, hematology, coagulation, and urinalysis)
- ECGs
- Vital signs
- Pulse oximetry

In general, long term safety analysis will be performed in a pooled fashion. All safety data will be presented in individual subject data listings. Only descriptive analyses of safety data will be performed.

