6.2 Sample Size and Power

The primary objective of the study is the evaluation of the long-term safety and tolerability of ELX/TEZ/IVA. This is an OLE study that will enroll subjects who did not discontinue study drug during the Treatment Period in parent study (445-116) and meet eligibility criteria. Approximately 108 subjects are expected to enroll in this OLE.

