8.4 Safety Analysis

The primary objective of the study is the evaluation of long-term safety and tolerability of TC. All safety analyses will be based on the TE Period in the OLE for subjects in the OL-SS. The overall long-term safety profile of study drug will be assessed in terms of the following safety and tolerability endpoints:

- Treatment-emergent adverse events (TEAEs)

- Clinical laboratory values
- Standard 12-lead ECGs
- Vital signs
- Pulse oximetry

Only descriptive analysis of safety will be performed, and no statistical testing will be performed.

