8.4.3 Electrocardiogram

For the following ECG measurements during the TE Period of OL-SS, a summary of observed values and change from baseline values will be provided at each visit (in msec): RR interval, PR interval, QT interval, and QTcF interval, QRS duration, and Heart Rate (beats per minute).

The number and percentage of subjects meeting at least 1 threshold analysis criterion during the TE Period of OL-SS will be summarized overall. The threshold analysis criteria are provided in [Appendix E](#).

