8.4.4 Vital Signs

For the vital sign measurements during the TE Period of OL-SS, the observed values and change from baseline values will be summarized at each visit. The following vital signs parameters will be summarized: systolic and diastolic blood pressure (mm Hg), body temperature ($^{\circ}$ C), pulse rate (beats per minute), and respiratory rate (breaths per minute).

The number and percentage of subjects meeting at least 1 threshold analysis criterion during the TE Period will be summarized. The threshold analysis criteria are provided in [Appendix E](#).

In addition, a listing containing individual subject vital signs values will be provided. This listing will include data from both scheduled and unscheduled visits.

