8.4.5 Pulse Oximetry

For the percent of oxygen saturation measurements using pulse oximetry during the TE Period for OL-SS, a summary of observed values and change from baseline values will be provided at each visit.

The number and percentage of subjects with shift changes from baseline category (classified as normal/missing or low according to the reference range) to the category at the lowest percent of oxygen saturation during the TE Period for OL-SS will be summarized. The reference range for normal oxygen saturation is specified as >95%, and ≤95% for low oxygen saturation.

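### Threshold tables for non-liver laboratory tests, blood pressure, heart rate, QRS and absolute QTc do not by themselves separate pre-existing from new or worsened abnormality

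*SAP*

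**What the plan says.** The study has no concurrent control (Protocol 9.2: "This is an open-label study"). Safety is the primary endpoint and is pooled and descriptive: "In general, long term safety analysis will be performed in a pooled fashion" (Protocol 12.3.4) and "Only descriptive analysis of safety will be performed, and no statistical testing will be performed" (SAP 8.4).

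The counting rule is the same in three places. SAP 8.4.2 counts subjects whose laboratory values meet at least one criterion in the TE Period. For ECG, SAP 8.4.3 has "The number and percentage of subjects meeting at least 1 threshold analysis criterion during the TE Period of OL-SS will be summarized overall". For vital signs, SAP 8.4.4 has "The number and percentage of subjects meeting at least 1 threshold analysis criterion during the TE Period will be summarized". Protocol 12.3.4.2 to 12.3.4.4 agree. None of these requires the baseline value to lie inside the limit or the value to have worsened.

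Baseline enters the categorical tables in only four places:

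- SAP 8.4.2: "The threshold analysis shift from baseline will also be summarized for selected LFT laboratory parameters" (the selected parameters are not named in that sentence).
- SAP 8.4.5: a shift table for oxygen saturation, with the baseline category "classified as normal/missing or low according to the reference range".
- Appendix E, PR: an absolute value combined with an increase of at least 20 ms.
- Appendix E, QTc: separate rows for increases of 30-60 ms and of more than 60 ms.

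SAP 8.1 defines a TC safety baseline, the last non-missing value before the first ELX/TEZ/IVA dose in either study.

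**The concern.** With no control arm, the subject's own value before ELX/TEZ/IVA is the main internal reference for the threshold tables. Several cut-offs are ones a subject could already exceed before treatment: systolic pressure above 120 mmHg, diastolic pressure above 80 mmHg, or any value just above or below the laboratory's normal range. Such a subject enters the count whenever one later value also meets the criterion, and the table does not show that the finding was there before.

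The plan uses baseline elsewhere. A treatment-emergent adverse event must be new or worsened, PR needs an increase, and liver tests and oximetry get shift tables. The SAP gives no reason for treating the remaining parameters differently. At stake is how readily the threshold tables, which form part of the primary endpoint, can be interpreted.

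Oximetry has a related, smaller flaw. A subject with no baseline reading who is later low is tabulated in the same row as one who moved from normal to low.

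**Working it through.** **1. Criteria checked against baseline use (Appendix E; SAP 8.4.2 to 8.4.5)**

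| Parameters | Baseline in the criterion | Shift table |
|---|---|---|
| Selected liver tests | no | yes |
| Other chemistry, hematology, coagulation | no | no |
| SBP, DBP | no | no |
| HR, QRS, absolute QTc | no | no |
| PR; QTc increase | yes | no |
| Oxygen saturation | not in Appendix E | yes |

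Rows 2 to 4 are the gap.

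**2. Scheduled post-baseline readings (Protocol Table 3-1; SAP Appendix A)**

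- Chemistry, hematology, vital signs: Weeks 4, 8, 16, 24, 36, 48, 60, 72, 84, 96 = 10, plus Safety Follow-up = 11.
- ECG, which also supplies the heart-rate criterion: Weeks 8, 16, 24, 48, 72, 96 = 6, plus Safety Follow-up = 7.
- Coagulation: Weeks 24, 48, 72, 96 = 4, with no follow-up sample.

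For the first two groups these are scheduled maxima. Follow-up falls at 28 ± 7 days and the TE Period ends by day 28, so some follow-up readings lie outside it. Some subjects have no separate follow-up visit (Protocol 9.1.2).

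**3. Illustration**

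The plan gives no figure to reproduce. The only number it supplies is the expected enrolment: "Approximately 108 subjects are expected to enroll in this OLE". The following are assumptions: the share p of single readings beyond the cut-off (5% or 10%), the within-subject correlation ρ (0.5, 0.7 or 0.9), normal values, and no drug effect or time trend.

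Model: Y = √ρ·b + √(1−ρ)·e, with b and e standard normal and cut-off t = z(1−p).

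- Chance that one reading is abnormal, given b: q = 1 − Φ[(t − √ρ·b)/√(1−ρ)].
- Counted over K readings: A = E[1 − (1−q)^K].
- Counted and abnormal at baseline: B = E[q·{1 − (1−q)^K}].
- Pre-existing share = B/A.
- Crossings among baseline-normal subjects = (A − B)/(1 − p).

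Example, p = 10%, ρ = 0.7, K = 11: A = 32.1% and B = 9.1%, so B/A = 28%. In 108 subjects, 108 × 0.321 = 34.7 are counted and 108 × 0.091 = 9.8 of them are pre-existing.

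Each cell gives the percentage of subjects counted, then the percentage of those already abnormal at baseline (numerical integration):

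| K | p | ρ = 0.5 | ρ = 0.7 | ρ = 0.9 |
|---|---|---|---|---|
| 11 | 5% | 25.9; 14.9 | 19.3; 22.4 | 11.8; 40.0 |
| 11 | 10% | 41.9; 20.5 | 32.1; 28.3 | 21.0; 45.8 |
| 7 | 5% | 20.3; 16.8 | 15.9; 25.4 | 10.5; 43.9 |
| 7 | 10% | 34.5; 22.7 | 27.4; 31.4 | 18.9; 49.7 |
| 4 | 5% | 14.4; 19.3 | 12.0; 29.4 | 8.8; 49.4 |
| 4 | 10% | 25.9; 25.7 | 21.7; 35.8 | 16.3; 54.9 |

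Fewer readings lower the count but raise the pre-existing share.

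Rare criterion, p = 1%, K = 11: 3-7% of subjects are counted and 8-31% of those are pre-existing, which is at most about 1 subject in 108.

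**4. What a baseline split leaves behind**

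With p = 5%, ρ = 0.7 and K = 11, B = 4.3%. Then (19.3 − 4.3)/95 gives about 16% of baseline-normal subjects crossing the cut-off by chance alone.

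**5. Which ECG baseline**

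The ECG rows of the Appendix A window table refer to the TC safety baseline of SAP 8.1. Item 5 of the derived variables in the same appendix instead takes the last measurement before the first study-drug dose in the Treatment Period. If that means this study's Treatment Period, then for a subject who took ELX/TEZ/IVA in the parent study the first is an off-drug value and the second need not be.

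**The case against.** The strongest reply is that the plan loses nothing and claims little. The threshold tables count subjects who meet a criterion. They do not label those subjects as having adverse events or attribute the values to drug, and nothing is tested. Baseline is used throughout the rest of the safety analysis. Adverse events must be new or worsened (SAP 8.4.1), and assessments become adverse events on clinically significant worsening from baseline (Protocol 13.1.1.2). Change from baseline is summarised by visit for continuous laboratory tests, ECG and vital signs, and individual listings are planned. A reader can find the pre-existing cases. Limiting shift tables to liver tests also matches the named special-interest risk of transaminase elevation (SAP 8.4.1.1).

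Most of this stands. A reader might infer that the plan treats pre-existing abnormality as drug-caused, or that the primary endpoint cannot separate the two. The documents support neither inference. What remains is narrower: visit-level mean changes do not show which threshold cases are new, and rebuilding that from listings is not a planned analysis.

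Two further objections also stand. Prevalences of 5-10% cannot be applied across Appendix E, where some rows are extreme (creatine kinase above 10 times the upper limit, QTc of 500 ms or more). And a baseline split does not remove chance crossings, as step 4 shows. On oximetry, missing baselines should be uncommon, because baseline takes the most recent non-missing value.

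**Conclusion.** The point holds as a gap in tabulation. For non-liver laboratory tests, SBP and DBP, HR, QRS and absolute QTc, the threshold tables ignore baseline status and so cannot, taken alone, distinguish pre-existing from new or worsened abnormality. The other planned outputs only partly make up for this.

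Under the assumed inputs, pre-existing cases make up 15-46% of those counted with 11 readings, 17-50% with 7 and 19-55% with 4. These ranges show the mechanism. They do not size the problem in this trial, because the documents give no prevalence and no correlation.

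A reader might also infer that subjects newly crossing a limit, once separated out, would measure a drug effect. That does not follow: repeated readings without a control produce new crossings by chance.

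**What to change.** - In SAP 8.4.2 to 8.4.4, extend the planned liver-test shift format to the Appendix E parameters listed in the verdict: TC-safety-baseline category by worst TE Period category, among subjects with both values, with pre-existing, new and worsened cases shown separately.
- State beside these tables that new crossings over repeated readings include chance crossings and are not in themselves evidence of a drug effect.
- Before building the ECG table, reconcile Appendix A item 5 with the TC safety baseline in SAP 8.1. The PR and QTc-increase rows depend on the same choice.
- In SAP 8.4.5, give missing baseline its own row.
- Optional: add a shift to the last on-treatment value, for which SAP 8.1 already provides. It is less exposed to taking the worst of many readings.

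The cost is SAP wording before database lock and a few more tables from existing data. Nothing new is collected.
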